## 14.7.2 Specific Strategies

## ● For PEF and FEV₁:

- o If a patient is unable to provide three acceptable blows, the best available single reading will be used (if at least one acceptable effort exists).
- o If no valid readings can be obtained from either the new device or reference method, that data point will be recorded as **missing**.

#### For HR and RR:

- o If standard or new device readings fail, a second attempt will be made immediately.
- o If still unsuccessful, the observation will be marked as **missing**.

## 14.7.3 Statistical Treatment of Missing Data

## Primary Analyses:

- Analyses (Bland-Altman plots, ICC calculations, proportion within limits) will be conducted using **complete cases only** (i.e., patients with valid paired measurements for the parameter being assessed).
- o No imputation of missing PEF, FEV1, HR, or RR values will be performed in the primary analysis.

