## 14.4 Sample Size Calculation

## **14.4.1 PEF Sample Size Calculation** (to show lower 95% CI bound ≥80%)

Study goal:

- True success proportion p1
- Null threshold (target to exceed) p0=0.80
- Type I error (2-sided): α=0.05
- Power:  $1-\beta=0.90$
- Use **Wilson score CI** to test whether lower bound ≥ 0.80.

Approximate approach (one-sample proportion power analysis)

We can approximate using a **one-sample proportion test** (binomial test of  $H_0$ : p = 0.80 vs  $H_1$ :  $p = p_1 > 0.80$ ):

$$n = rac{\left[z_{1-lpha/2}\sqrt{p_0(1-p_0)} + z_{1-eta}\sqrt{p_1(1-p_1)}
ight]^2}{(p_1-p_0)^2}$$

This gives the approximate number of *paired comparisons* (subjects) needed.

Where:

- $z1-\alpha/2=1.96$  for  $\alpha=0.05$
- $z1-\beta=1.2816$  for 90% power

Example calculation

Expected true agreement proportion p1=0.90.

Then:

$$p_0 = 0.80, \quad p_1 = 0.90 \ n = rac{(1.96\sqrt{0.8 imes 0.2} + 1.2816\sqrt{0.9 imes 0.1})^2}{(0.9 - 0.8)^2}$$

Computing:

$$\sqrt{0.8 \times 0.2} = 0.4, \quad \sqrt{0.9 \times 0.1} = 0.3$$

$$n = \frac{(1.96(0.4) + 1.2816(0.3))^2}{(0.1)^2} = \frac{(0.784 + 0.384)^2}{0.01} = \frac{1.168^2}{0.01} = \frac{1.364}{0.01} = 136.4$$

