## Sensitivity Analyses:

- Sensitivity analyses will be considered if >10% of data for any parameter are missing.
  - For PEF, imputation methods such as last observation carried forward (LOCF) or single imputation using median of available efforts may be considered for exploratory purposes
  - For usability outcomes, missing questionnaire responses will not be imputed; proportions will be based on available data.

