# 14.10 Estimand Table

Component	PEF	FEV 1	RR	HR
Treatment	Measurement using new device	Measurement using new device	Measurement using new device	Measurement using new device
Comparator	Vitalograph spirometer	Vitalograph spirometer	Manual count	Pulse oximeter
Population	Adults ≥18 years presenting to ED with respiratory / cardiorespiratory symptoms	Same as PEF	Same as PEF	Same as PEF
Variable (Endpoint)	Peak Expiratory Flow; PEF (L/min)	Forced Expiratory Volume in One Second; FEV 1 (L)	Respiratory Rate; RR (Breaths per minute)	Heart Rate; HR (beats per minute)
Summary Measure	Mean bias, 95% Limits of Agreement, % within ± 20% of reference	Mean bias, 95% Limits of Agreement, % within ±10%	Mean bias, 95% Limits of Agreement, % within ±10%	Mean bias, 95% Limits of Agreement, % within ±10%
Handling of Missing Data	Exclude invalid readings; perform sensitivity analysis if needed	Same as PEF	Same as PEF	Same as PEF
Intercurrent Events	Poor technique, device malfunction	Spirometry effort failure, device errors	Talking during measurement, movement artefact	Movement artefact, device connectivity issues
Interpretation	Agreement sufficient for clinical decision support at bedside	Agreement comparable to spirometry for diagnosis and monitoring	Agreement sufficient for respiratory distress assessment and monitoring	Agreement sufficient for accurate triage and monitoring

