## 16.8 Audits and Inspections

## 16.8.1 Protocol compliance

The Essential Documents (all documentation in the ISF and subjects' source documentation) at the clinical site will be thoroughly reviewed by the study monitor to assess protocol compliance and validity of trial conduct. If the monitor detects any protocol deviations, these will be discussed with the Chief Investigator and relevant members of the site team to determine the reason for the deviation and to mitigate its future occurrence. Any deviations will be corrected where possible. If it is not possible to correct the deviation, the details will be highlighted to the Sponsor to determine whether data is still usable or should be eliminated from the analysis. The deviations will be classified as minor or major and will be recorded in the monitoring visit report. The study monitor will provide re-training to study team members following all protocol deviations. If a member of the study team continues to deviate from the requirements of the protocol despite attempts by the Sponsor to re-train the individual, the Sponsor may request a replacement person to carry out the role with any further participants.

The Sponsor understands that accidental protocol deviations can occur from time to time. If a member of the site team realises an accidental protocol deviation has occurred, they should immediately notify the Chief Investigator at site and the Sponsor representative, providing details of what has happened and how it differs from the approved protocol. The CI and Sponsor will discuss whether the deviation can be rectified in any way. If it is not possible to correct the error, the Sponsor will decide whether the data is still useful or whether it should be excluded from the analysis.

All protocol deviations (minor and major) must be documented for full transparency, using a Protocol Deviation Reporting Form (blank PD reporting forms will be provided in the ISF). A deviation will be considered major if the Sponsor deems it to have jeopardised the integrity of the data in any way. Details of major deviations will be reported to the Ethics Committee.

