## 20.3.7 Results Screen for Breath Scan (PEF, FEV₁ and RR)

The three sets of results for PEF, FEV1 and RR will appear on the Results screen within 2 to 3 minutes of the measurements being taken, depending on the speed of the internet connection.

If any of the three sets of measurements have been unsuccessful and there are missing results, the CI/RN should ask the subject to repeat the Breath Scan. If there are any obvious reasons as to why the scan did not work, these will be noted by the CI/RN along with the need to perform a repeat scan. When the scan has been repeated, the results screen with be updated to include all successful measurements on the same screen.

A maximum of 3 retry Breath Scans should be attempted as needed to produce 3 results for each of the 3 parameters PEF, FEV1 and RR. If there are still missing data after 3 retry Breath Scans have been carried out, the missing results will be recorded as 'Not Available' (NA). The number of additional scans needed will be recorded.

Confirmation of the results for PEF, FEV1 and RR will subsequently be sent to the CI/RN as a PDF document for filing in the subject's medical notes to enable verification.

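### The PEF success rule leaves out subjects in whom the device gives no reading, nothing else in the rule limits such failures, and the fallback imputation named for PEF has no data to work on

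*Protocol*

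**What the plan says.** Section 14.3.2 takes each subject's paired PEF values, checks whether the device is within 20% of the spirometer, and calls the study positive for this outcome if the Wilson lower bound of the proportion is at least 80%. Section 14.7.3 limits Bland-Altman, ICC and this proportion to "patients with valid paired measurements for the parameter being assessed", with no imputation in the primary analysis.

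Section 14.7.2 defines when PEF is missing. With fewer than three acceptable blows, "the best available single reading will be used (if at least one acceptable effort exists"; only if a method yields no valid reading is the data point missing. Section 14.7.1 expects equipment or technical failure among the main causes. The estimand table (14.10) lists device malfunction as an intercurrent event for PEF and gives the handling as "Exclude invalid readings; perform sensitivity analysis if needed".

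If more than 10% of a parameter is missing, sensitivity analyses will be considered. For PEF the methods named are "last observation carried forward (LOCF) or single imputation using median of available efforts", as exploratory options. Section 14.8 summarises the amount, pattern and reasons for missing data.

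Section 14.4.1 covers capture failures by recruiting up to 160 subjects, to reach 150 analysable sets.

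**The concern.** For a diagnostic app, failing to return a result is part of performance. Here it is handled like a withdrawal: the subject is replaced through over-recruitment and drops out of the figure that decides success. No second criterion caps the failure rate, and the rule names no minimum number of valid pairs.

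The estimand table interprets a positive PEF result as agreement good enough to support decisions at the bedside. A complete-pair proportion supports that only for subjects in whom a reading was obtained. A user who picks up the device also needs to know how often it gives a usable reading that agrees. If failures are more than rare, the two figures differ materially, and the plan as written does not require the second to be shown.

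**Working it through.** **1. The plan's own figure.** Inputs from 14.4.1: "Type I error (2-sided): α=0.05", p0 = 0.80, p1 = 0.90, power 0.90.

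n = [1.96·√(0.8·0.2) + 1.2816·√(0.9·0.1)]² / (0.10)² = (0.784 + 0.384)² / 0.01 ≈ 136.5, rounded up to 137. This reproduces the stated 137. Exactly, the Wilson rule at n = 137 requires 119 successes, with one-sided alpha 0.0245 at p0 and power 0.910 at p1. The calculation concerns subjects with a valid pair; capture failures enter only through the margin to 160.

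**2. Same successes, two denominators.** Wilson lower bound:

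L = [p + z²/2n − z·√(p(1−p)/n + z²/4n²)] / (1 + z²/n), with z = 1.96.

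- 130/150: p = 0.8667. L = (0.8667 + 0.0128 − 1.96·0.02851)/1.0256 = 0.803. Positive; 130 is the smallest passing count at 150.
- 130/160: p = 0.8125. L = (0.8125 + 0.0120 − 1.96·0.03146)/1.0240 = 0.745. Not positive.

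The second line assumes that all 10 subjects outside the 150 are device failures with a valid reference reading. Away from the pass boundary, at the planned 90% agreement, 135/150 has L = 0.842, while 135/160 = 84.4% has L = 0.780. The point estimate stays above 80%, but the bound does not.

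**3. Break-even failure rate.** With 90% agreement among valid readings and device-failure rate f, the all-subject rate is 0.90(1 − f). It equals 0.80 at f = 1 − 0.80/0.90 = 11.1%.

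**4. Chance of meeting the 80% rule.** Exact binomial, 160 subjects all with a valid reference reading, 90% agreement among valid device readings. The values of f are assumptions. With all 160 in the denominator the rule needs 138 successes.

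| f | All-subject rate | Complete pairs | Failure counted as not within limits |
|---|---|---|---|
| 0 | 90.0% | 0.951 | 0.951 |
| 2% | 88.2% | 0.934 | 0.815 |
| 5% | 85.5% | 0.928 | 0.448 |
| 6.25% | 84.4% | 0.924 | 0.299 |
| 10% | 81.0% | 0.913 | 0.052 |
| 11.1% | 80.0% | 0.909 | 0.026 |

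The complete-pair result barely moves with f; the loss comes only from fewer pairs.

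**5. The fallback.** Take a subject with missing device PEF.
- Median of available efforts: by 14.7.2 a single acceptable effort would have been used as the value, so a missing PEF has no acceptable effort from that method.
- Last observation carried forward: the study has one visit, so there is no earlier observation.

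Where efforts do exist, the value is not missing and nothing needs imputing.

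**6. Retries.** For HR and RR, 14.7.2 states: "If standard or new device readings fail, a second attempt will be made immediately", and then missing. For the Breath Scan, which yields RR, 20.3.7 states: "A maximum of 3 retry Breath Scans should be attempted as needed to produce 3 results". Section 20.3.8 likewise allows three additional Pulse Scans for HR. The two sets of statements define missingness differently for HR and RR.

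**The case against.** The strongest reply is that the primary endpoint (10.1, 14.1.1) is agreement in measurement. A subject without a device value has no difference to assess, so complete pairs are the natural set. That stands: the complete-pair proportion is a valid agreement measure, and counting failures as non-agreement answers a different, composite question.

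Nor are failures hidden. Section 14.8 reports missing data and reasons, 20.3.7 records extra scans, 14.3.4 summarises error rates, 15.4 requires device deficiencies to be reported, and 10.2 makes unsuitable subgroups and conditions secondary endpoints. All of this is true, but none of it bears on the positive decision or yields the all-subject proportion. The imputation methods are exploratory examples and cannot alter the primary result; their fault is that they leave the plan without a workable sensitivity analysis.

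A reader might infer more than the documents support:

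- *That a passing study could conceal a clear failure.* 119/137 passes (lower bound 80.2%), and 119/160 is 74.4%. But this treats all 23 other subjects as device failures. The margin in 14.4.1 also covers withdrawals and other failures, 14.7.1 lists patient inability and time pressure, and 13.3 removes withdrawals from the analysis. The Wilson interval for 119/160, 67.1% to 80.5%, also includes 80%, so it misses the rule without showing a rate below 80%.
- *That failures must fall in sicker subjects.* Coughing and movement are named as recording problems (11.0, 20.3.4), but 7.3 says that subjects often find the device easier when clinically worse. The direction is unknown.
- *That the retry conflict affects the primary endpoint.* For PEF, 14.7.2 gives no retry count and 20.3.7 alone does, so there is no conflict.

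**Conclusion.** The point holds as a limit on what a positive PEF result shows. Device failures leave the denominator, the success rule does not constrain them, and the fallback named for PEF cannot be carried out. It does not show that the agreement analysis is invalid or that the device would fail.

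The size depends on a failure rate that the protocol does not give. If the planned shortfall of 10 in 160 (6.25%) were entirely device failure, a bare pass at 130/150 would become 81.3% with a lower bound of 74.5%. At 90% agreement among valid readings, failure in about 11% brings the all-subject rate down to 80%, while the complete-pair rule would still be met about 91% of the time. If failures are very rare, the two analyses nearly coincide.

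The HR/RR retry mismatch and the deviation rule in 16.8.1 are secondary. Under the latter, where a deviation cannot be corrected, "the Sponsor will decide whether the data is still useful or whether it should be excluded from the analysis". Deviations are documented and major ones go to the ethics committee, but nothing requires the decision to be made without sight of the paired values.

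**What to change.** - Keep the complete-pair proportion, Bland-Altman and ICC as the agreement analyses.
- In 14.7.3, add a pre-specified analysis, run whatever the amount of missing data and reported beside the primary result. Its denominator is all subjects with a valid reference reading; no valid device reading after the permitted retries counts as not within limits. Reference failures stay out.
- Report the device-failure rate with a Wilson interval.
- In 14.10, limit the bedside interpretation to subjects in whom a reading is obtained, unless the added analysis also supports it.
- Delete last observation carried forward and median imputation.
- Secondary: reconcile the HR/RR retry statements in 14.7.2 with 20.3.7 and 20.3.8, and have exclusions under 16.8.1 decided without sight of the paired values.

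This costs wording in 14.7, 14.10, 16.8.1 and the retry passages, with no new data or subjects. The downside is a possibly less favourable figure beside the headline.

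If the sponsor instead makes failure-as-not-within-limits the primary endpoint, the cost is larger and the power in 14.4.1 must be restated. At an assumed 5% failure rate, power with 160 subjects is about 0.45. The protocol's formula with p1 = 0.90 × 0.95 = 0.855 gives n = [0.784 + 1.2816·√(0.855·0.145)]² / 0.055² ≈ 504.4, so 505 subjects; at 2% (p1 = 0.882) it gives 214.

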## Sensitivity Analyses:

- Sensitivity analyses will be considered if >10% of data for any parameter are missing.
  - For PEF, imputation methods such as last observation carried forward (LOCF) or single imputation using median of available efforts may be considered for exploratory purposes
  - For usability outcomes, missing questionnaire responses will not be imputed; proportions will be based on available data.

## 14.8 Reporting

- The amount and pattern of missing data will be summarized by parameter (PEF, FEV1, HR and RR).
- The reasons for missing data (if known) will be categorized and reported descriptively.
- The potential impact of missing data on study conclusions will be discussed in the final study report.

## 14.9 Example Estimated Results Table

Parameter	Performance Range	Likely Performance of Device  (% Within Limits of Reference Values)	Bias Target	Expected Acceptable Level Of Agreement
PEF	350 – 700 L/min	≥ 80% within ± 20%	± 10%	± 20%
FEV 1	2-5L	≥ 95% within ± 10%	± 0.1L	± 0.2 – 0.25 L
RR	6 – 20 breaths per minute (Bpm)	≥ 95% within ± 10%	± 2 Bpm	± 4 Bpm
HR	50 – 120 beats per minute (bpm)	≥ 95% within ± 10%	± 5 bpm	± 2 bpm

# 14.10 Estimand Table

Component	PEF	FEV 1	RR	HR
Treatment	Measurement using new device	Measurement using new device	Measurement using new device	Measurement using new device
Comparator	Vitalograph spirometer	Vitalograph spirometer	Manual count	Pulse oximeter
Population	Adults ≥18 years presenting to ED with respiratory / cardiorespiratory symptoms	Same as PEF	Same as PEF	Same as PEF
Variable (Endpoint)	Peak Expiratory Flow; PEF (L/min)	Forced Expiratory Volume in One Second; FEV 1 (L)	Respiratory Rate; RR (Breaths per minute)	Heart Rate; HR (beats per minute)
Summary Measure	Mean bias, 95% Limits of Agreement, % within ± 20% of reference	Mean bias, 95% Limits of Agreement, % within ±10%	Mean bias, 95% Limits of Agreement, % within ±10%	Mean bias, 95% Limits of Agreement, % within ±10%
Handling of Missing Data	Exclude invalid readings; perform sensitivity analysis if needed	Same as PEF	Same as PEF	Same as PEF
Intercurrent Events	Poor technique, device malfunction	Spirometry effort failure, device errors	Talking during measurement, movement artefact	Movement artefact, device connectivity issues
Interpretation	Agreement sufficient for clinical decision support at bedside	Agreement comparable to spirometry for diagnosis and monitoring	Agreement sufficient for respiratory distress assessment and monitoring	Agreement sufficient for accurate triage and monitoring

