In addition, we have also noted that as well as offering multiplication in accessibility to such clinical data the smartphone device offers considerable benefits to users in ease of capture of this data. We have also recognised for respiratory functions, that worsening clinical condition increases variation in an individual's sets of readings but on the other hand that often subjects find using the new device easier when they are clinically worse. Thus, as well as looking at parameter agreement we have included an analysis of 'usability' which we will link to clinical status.

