#### 11.0 STUDY DESIGN

This study will take place at a single investigational site, namely Cambridge University Hospitals NHS Foundation Trust (CUH) in the Emergency Department, where the research team has extensive experience in performing clinical research studies in similar fields. The study will be conducted in compliance with the protocol, principles of Good Clinical Practice (GCP) and the applicable regulatory requirements.

Subjects will be male or female, aged 18 years and above. Subjects must be able to sit up and read, understand and write in English. Subjects with and without respiratory or cardiorespiratory symptom/s will be included. All participants will be required to sign an Informed Consent Form (ICF) and be allocated a unique study number by the Chief Investigator (CI)/Research Nurse (RN) or a suitably trained designee. Subjects will only be identified by the study number in all trial-related documentation i.e. there will be no patient identifiable information (PID) recorded for study purposes. At the hospital site, a subject identification log will be maintained to link the study subject number to individual PID, which will only be accessible to the subjects' clinical research team. This information will not be made available to the Sponsor. However, the study monitor will require access to ensure the correct subject's medical notes are reviewed during source data verification (SDV). The subjects will be made aware of this during the informed consenting process.

There are no treatment arms in the study. Each subject will be tested using standard clinical equipment to produce control data and by purpleDx to produce investigational data.

At the hospital visit, the following data points will be collected for each subject by the CI/RN or designee:

- Unique Subject Study Number
- Sex at birth
- Age in years

- Date of assessment
- Height in cm
- Weight in kg
- Chest circumference in cm (see Appendix 7)
- Skin tone (measured using device provided by Sponsor); see Fitzpatrick scale in Appendix 4
- Emergency Care Data Set (ECDS) presentation code
- Discharge diagnosis confirming chest illness
- 7, 14 and 30-day mortality status
- Smoking status (and number of pack years if smoker)
- Medical conditions (up to 5 relevant respiratory or cardiorespiratory) conditions, cardiac conditions, skeletal conditions e.g. scoliosis / mobility problems) to describe the population for intended use

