## 12.0 SUBJECT ELIGIBILITY CRITERIA

#### 12.1 Inclusion Criteria

- 1) Sex at birth classified as male or female
- 2) 18 years of age and above, presenting to CUH Emergency Department
- 3) Able to read and understand the patient information sheet in English
- 4) Capacity and ability to sign an informed consent form
- 5) With or without respiratory or cardiorespiratory symptom/s

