#### 12.2 Exclusion Criteria

- 1) Unable to sit up i.e. cannot lie completely flat (supine)
- 2) Known pregnancy in women of child-bearing potential (WOCBP)
- 3) Unable to comply with the requirements of the investigation in any way
- 4) Prisoners or young offenders

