#### 14.2 Data Collection

• Participants: Adults (≥18 years) presenting to the ED with or without respiratory or cardiorespiratory symptoms.

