## 20.2 Appendix 2: Images of Subject Using purpleDx

The purpleDx app should be used with the subject sitting upright or reclining on a bed/trolley (with angle of incline recorded). For the trial purposes, the subject cannot lie completely flat (supine). The smartphone should be immobilised using a phone stand or by leaning it against a sturdy, static object.

[figure not shown]

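### The estimand table names symptomatic ED patients as the population, but enrolment, the 137 pairs and the primary success rule cover patients with or without symptoms

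*Protocol*

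**What the plan says.** The estimand table (Protocol section 14.10) sets the PEF population as "Adults ≥18 years presenting to ED with respiratory / cardiorespiratory symptoms" and carries the same population over to FEV1, RR and HR. Its interpretation row for PEF concerns decision support at the bedside.

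The other passages that define the population are wider:
- Section 12.1, criterion 5, repeated in the synopsis: "With or without respiratory or cardiorespiratory symptom/s".
- Section 11.0: "Subjects with and without respiratory or cardiorespiratory symptom/s will be included".
- Section 14.2, within the same statistical section as the estimand table: adults "presenting to the ED with or without respiratory or cardiorespiratory symptoms".

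The primary rule in section 14.3.2 takes the proportion of all paired subjects whose two PEF values lie within 20% of each other. The result is positive if the lower Wilson bound is at least 80%. Section 14.4.1 derives 137 pairs with a single true proportion of 0.90 for everyone, targets 150 analysable sets and caps recruitment at 160. Neither section restricts the count to symptomatic subjects or sets a quota.

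On a separate matter, exclusion criterion 1 (section 12.2 and the synopsis) reads "Unable to sit up i.e. cannot lie completely flat (supine", while Appendix 2 says "For the trial purposes, the subject cannot lie completely flat (supine" in describing how the app is used.

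**The concern.** An estimand states for whom the conclusion is drawn. Here it names patients with symptoms, while the test that decides the trial is run on a mixture whose composition is left to chance. Two readings are open to the analyst:

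1. Analyse everyone, as sections 14.2 to 14.4 imply. The result then describes the mixture, and a pass can be carried by subjects without symptoms while the estimand table attributes it to those with them.
2. Analyse only the symptomatic subjects, as section 14.10 implies. The number of pairs then falls below the number on which the power was calculated.

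If the choice is left open until the data are in, the primary analysis population is chosen after the event. The two halves of exclusion criterion 1 also describe different patients, so screening staff could apply it in different ways.

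**Working it through.** **The plan's own figure.** Inputs from section 14.4.1: p0 = 0.80, p1 = 0.90, two-sided α = 0.05 (z = 1.96), power 0.90 (z = 1.2816).

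n = (1.96×√(0.8×0.2) + 1.2816×√(0.9×0.1))² / (0.90 − 0.80)² = (0.784 + 0.3845)² / 0.01 = 136.5, rounded up to 137. The figure reproduces.

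**The exact rule.** The smallest count whose lower two-sided 95% Wilson bound reaches 0.80 is:
- n = 137: 119 successes. Chance of passing at a true 80% is 2.4%; power at 90% is 91.0%.
- n = 150: 130 successes. Chance of passing at a true 80% is 2.2%; power at 90% is 92.8%.

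The arithmetic is sound. What is unclear is which population it serves.

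**Reading 1: everyone pooled, 150 analysable.** The symptomatic share and the agreement in each group are not stated, so both are assumed. With 150s symptomatic subjects (rounded) at agreement pS and the rest at pO, the chance of a positive result is P(X + Y ≥ 130), where X and Y are independent binomials, computed exactly.

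| Symptomatic share (number) | pS 75%, pO 95% | pS 80%, pO 95% | pS 75%, pO 90% |
|---|---|---|---|
| 25% (38) | 93% | 98% | 49% |
| 50% (75) | 32% | 68% | 10% |
| 75% (112) | 2% | 20% | 1% |

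In every cell the symptomatic group does not exceed the 80% bar. For pS 75% and pO 95% the overall proportion is 0.25×0.75 + 0.75×0.95 = 0.90 at a 25% share, 0.85 at 50% and 0.80 at 75%. If pS = pO, the pooled test and a test in symptomatic subjects address the same proportion, and the discrepancy vanishes.

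**Reading 2: symptomatic subjects only, true agreement 90%, 150 analysable.** The last column is 137 divided by the share.

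| Symptomatic share (number) | Successes needed | Exact power | Power by the plan's formula | Analysable total for 137 symptomatic |
|---|---|---|---|---|
| 25% (38) | 36 | 25% | 29% | 548 |
| 50% (75) | 67 | 67% | 61% | 274 |
| 75% (112) | 98 | 85% | 82% | 183 |

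All three totals exceed the cap of 160 recruited.

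**Exclusion criterion 1.** No arithmetic applies. Being unable to sit up and being unable to lie flat are different conditions. Appendix 2 uses the same words, "the subject cannot lie completely flat (supine", as an instruction about position during the test. Read that way, the gloss in the criterion is a wording slip. Read literally, it excludes patients who cannot lie flat.

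**The case against.** The strongest reply is that one table cell disagrees with the synopsis, the design, the eligibility criteria and section 14.2, so the cell is most likely a drafting slip. Neither the primary endpoint (section 10.1) nor the primary objective (section 14.1.1) limits the claim to symptomatic patients. Once the cell is aligned, n = 137 stands. This is a fair account of how the discrepancy probably arose, and it means that power is lost only if the table overrides the enrolment text. It does not make the cell correct.

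The protocol also protects subgroups in part. Section 10.2 makes the search for unsuitable patient subsets a secondary endpoint, and section 8.1 commits to amending the intended-user description if one is found. That stands and shapes the fix, but it leaves the population of the primary conclusion unchanged.

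Three stronger readings might be inferred, and the documents support none of them:
- That the protocol itself says agreement is worse in symptomatic patients. Section 7.3 says "that worsening clinical condition increases variation in an" individual's sets of readings. This concerns repeat readings within a person, not device against reference. The same sentence adds that subjects often find the device easier to use when they are clinically worse, and worsening condition is not the same as having symptoms. Lower agreement in symptomatic patients is a possibility, not a statement of the protocol.
- That a misleading pass is likely. The same assumed 75% and 95% give anything from 93% to 2%, depending on a share that nobody has stated.
- That exclusion criterion 1 shifts agreement in the same direction. Nothing in the documents shows that it does.

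**Conclusion.** The plan is wrong as written: section 14.10 and the primary test name different populations, within the same statistical section. That conclusion needs no assumption.

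Its numerical consequence does. On the pooled reading, the chance of a pass when symptomatic agreement is only 75% ranges from about 93% to 2% for shares of 25% to 75%, taking 95% agreement in the others. It is lower if agreement in the others is lower. On the literal reading of section 14.10, power at a true 90% is about 67% rather than 90% if half of 150 subjects are symptomatic. If agreement is the same in both groups, or nearly all recruits are symptomatic, the pooled result serves either population.

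The trial remains a valid test for the population it enrols. The text should be corrected before the data are analysed. The exclusion wording is a separate, minor inconsistency.

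**What to change.** - In section 14.10, change the population for all four parameters to adults presenting to the ED with or without respiratory or cardiorespiratory symptoms. This matches enrolment and keeps n = 137.
- Report the PEF proportion within ±20% and its Wilson interval by symptom status, as part of the subgroup evaluation already planned in sections 8.1 and 10.2. Section 11.0 lists a presentation code and a discharge diagnosis but no symptom-status field, so the rule that classifies subjects from these items must be fixed before the data are seen.
- Reconcile the two halves of exclusion criterion 1, in section 12.2 and the synopsis, with each other and with Appendix 2.

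The cost is a change of wording, one classification rule and one extra table, with no new subjects or data items. The drawback is a less precise result for the symptomatic subset: with half of 150 subjects, the interval is wider by a factor of roughly √(150/75) = 1.41 at the same observed proportion.
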